12.1.4.1. Hypotheses

The null and alternative hypotheses are as follows:

H_0 : The all-cause mortality free-rate (survival rate) from 0-12 months $\leq 80.0\%$

H_A : The all-cause mortality free-rate (survival rate) from 0-12 months $> 80.0\%$

The null hypothesis (H_0) will be rejected if the lower one-sided 97.5% confidence bound for the all-cause mortality free-rate is greater than the performance goal of 80.0%.

12.1.4.2. Statistical Methods

When the final study subject reaches the final CIP required follow-up visit, the primary analysis will be performed based on the Kaplan-Meier method for the estimation of the 12-month all-cause mortality free-rate (survival rate) including the lower 97.5% confidence bound (computed based on log-log methodology). This Kaplan-Meier analysis will begin at the time of enrolment. Subjects that withdraw consent or are lost-to-follow-up prior to the 12-month endpoint evaluation will be censored at their date of last contact. All subjects actively enrolled will be included in the endpoint analysis.

The null hypothesis will be rejected and the endpoint considered met if the lower 97.5% confidence bound for the all-cause mortality free-rate (survival rate) at 12 months is greater than 80.0%.

Additionally, a Kaplan-Meier survival time-to-event curve along follow-up will be provided.

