All applicable eCRFs should be completed up to the point of subject withdrawal. Subjects who are "lost-to-follow-up" should have 3 documented failed phone call attempts to contact the subject as well as a certified letter sent to the subject without a response prior to study withdrawal or termination. A death note will need to be provided together with the serious adverse event (SAE) event description on the Adverse Event (AE) form. Additional data may no longer be collected after the point at which a subject has been withdrawn from the study or withdraws his/her consent, for whatever reason. All open AEs should be closed or documented as chronic or continuing at the end of the study. Data collected up to the point of subject withdrawal may be used. A Study Withdrawal eCRF page should be completed at this time. A retrospective cancelling of subject data collection should be expressed explicitly by the subject so that all data can be removed from the database.

10.3. *Subject Status and Classification*

Consent ineligible subject

A study subject who has signed informed consent but is found to not meet eligibility criteria will be considered a consent ineligible subject and will not count towards the enrolment ceiling. There are no follow-up or AE reporting requirements for consent ineligible subjects. The original signed informed consent must be maintained in the center's administrative file as original or e-copy as part of the hospital patient chart.

Active enrolled subject

A study subject who meets the eligibility criteria as per Section 9.2 and Section 9.3 and has signed and dated the subject informed consent form (ICF) is considered actively enrolled in the study. These subjects are followed in accordance with the CIP follow-up schedule and included in the foreseen study analysis. The original signed subject ICF and any applicable documentation must be maintained in the center's subject paper or electronic file. All applicable electronic Case Report Form (eCRFs) per the CIP must be completed.

10.4. *Enrolment Controls*

Centers are allowed to enroll up to 20% of subjects in each of the 4 defined Subject Cohorts. This translates into the following allowed maximum subject numbers per center:

- ICD:23 to 54 subjects*
- CRT-D: 19 to 50 subjects*
- PM/CRT-P:34 to 40 subjects
- Non-device:34 to 60 subjects
(ESC Guideline 2016 Indicated but not implanted)

* Variable; depending on the total number of enrolled subjects in this study cohort.

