12.1.3. Primary Endpoint for PM/CRT-P Treated Subjects

The primary endpoint for PM/CRT-P treated subjects is:

- All-cause mortality in subjects with a maximum of 3 risk factors (analyzed for MADIT II data⁷)

Based on previous CARE-HF study⁸, we estimate that 10% of the PM/CRT-P treated subjects will present an all-cause mortality within one year.

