12.1.3.2. Statistical Methods

When the final study subject reaches the final CIP required follow-up visit, the primary analysis will be performed based on the Kaplan-Meier method for the estimation of the 12-month all-cause mortality free-rate (survival rate) including the lower 97.5% confidence bound (computed based on log-log methodology). This Kaplan-Meier analysis will begin at the time of implant. Subjects that withdraw consent or are lost-to-follow-up prior to the 12-month endpoint evaluation will be censored at their date of last contact. All subjects actively enrolled will be included in the endpoint analysis.

The null hypothesis will be rejected and the endpoint considered met if the lower 97.5% confidence bound for the all-cause mortality free-rate (survival rate) at 12 months is greater than 80.0%.

Additionally, a Kaplan-Meier survival time-to-event curve along follow-up will be provided.

12.1.4. **Primary Endpoint for Non-device Subjects (ESC Guideline 2016 Indicated but not implanted)**

The primary endpoint for Non-device subjects (ESC Guideline 2016 Indicated but not implanted) is:

- All-cause mortality in the subject cohort with 2 to 5 predefined SCD driving risk factors.

Based on the MADIT II study², we estimate that 10% of the Non-device subjects (ESC Guideline 2016 Indicated but not implanted) will present an all-cause mortality within one year.

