12.1.6. Sample Size

The pre-specified primary endpoints sample sizes are outlined in **Error! Reference source not found.** The minimum required sample sizes to sufficiently power each primary endpoint at 90% and account for up to 20% attrition are lower than the final sample sizes.

The final sample sizes for the device cohorts (ICD: 117 to 270 subjects; CRT-D: 95 to 250 subjects; PM/CRT-P: 172 to 200 subjects) will ensure that there will be a sufficient number

of subjects to evaluate each primary endpoint, as well as provide ample data to characterize the safety, performance and efficacy profiles based on secondary and additional endpoints.

The final sample size for the non-device cohort (Non-device [ESC Guideline 2016 Indicated but not implanted]: 172 to 300 subjects) will ensure that there will be a sufficient number of subjects to compare the rate of sudden cardiac death in the non-device cohort with the rate of appropriately treated ventricular arrhythmias or sudden cardiac death in the defibrillator cohort (ICD, CRT-D).

In case of low enrollment rates, enrollment may be closed after the statistically required calculated minimum sample size was completed.

Table 12.1-1: Endpoint Sample Size Estimates

Endpoint	Measurement	Performance Goal Hypotheses ¹	Expected Performance ²	Power	Number of Subjects	
					Needed for Analysis	Required Minimum Sample size Enrolled for ≤20% Attrition
Primary Endpoint for ICD Treated Subjects	Ventricular arrhythmia ³ associated symptoms free-rate from 0 to 12 months	H_0 : Rate ≤ 85.0% H_A : Rate > 85.0%	95.0%	90%	93	117
Primary Endpoint for CRT-D Treated Subjects	Ventricular arrhythmia ³ associated symptoms free-rate from 0 to 12 months	H_0 : Rate ≤ 87.0% H_A : Rate > 87.0%	97.0%	90%	76	95
Primary Endpoint for PM/CRT-P Treated Subjects	All-cause mortality free-rate (survival rate) from 0 to 12 months	H_0 : Rate ≤ 80.0% H_A : Rate > 80.0%	90.0%	90%	137	172
Primary Endpoint for Non-device Subjects (ESC Guideline 2016 Indicated but not implanted)	All-cause mortality free-rate (survival rate) from 0 to 12 months	H_0 : Rate ≤ 80.0% H_A : Rate > 80.0%	90.0%	90%	137	172

¹ Hypothesis test based on a one-sided alpha level of 0.025; clinically accepted delta of 10%, subtracted from expected performance

² Determined from prior comparable studies

³ Appropriately treated

CRT-D = cardiac resynchronization therapy-defibrillator; ICD = implantable cardioverter-defibrillator;

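### Lost subjects are censored in the two mortality tests and no later data may be collected on them, so informative loss would raise the false-pass rate above 2.5% with no planned check

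*Combined protocol and SAP*

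**What the plan says.** - **Analysis.** Sections 12.1.3.2 (PM/CRT-P) and 12.1.4.2 (Non-device) use the Kaplan-Meier 12-month survival estimate with a log-log lower 97.5% bound. The goal is met if that bound exceeds 80.0%. On loss, both say: "Subjects that withdraw consent or are lost-to-follow-up prior to the 12-month endpoint evaluation will be censored at their date of last contact".
- **Data after withdrawal.** Section 10.2 makes three failed calls and a certified letter the steps before a lost subject is withdrawn or terminated. It then says: "Additional data may no longer be collected after the point at which a subject has been withdrawn from the study or withdraws his/her consent", whatever the reason. A lost subject who never withdrew consent is therefore covered.
- **Exception.** After withdrawal for device safety or performance problems, the investigator asks permission to follow the subject outside the study (also Section 10.2). This cannot apply to the Non-device cohort.
- **Planning figures.** Expected one-year mortality is 10% in each cohort: "we estimate that 10% of the PM/CRT-P treated subjects will present an all-cause mortality within one year" (Section 12.1.3) and "we estimate that 10% of the Non-device subjects" (Section 12.1.4). Section 12.1.6 sets sample sizes to "sufficiently power each primary endpoint at 90% and account for up to 20% attrition".
- **Synopsis.** Under Statistical Test Method, the same endpoint is the proportion of actively enrolled subjects alive at 12 months. How lost subjects count is not stated.
- **Not found.** The documents contain no vital-status check after loss and no sensitivity analysis for loss. Section 12.1.5 and Section 12.3 defer details of secondary, additional and propensity analyses to a SAP. The primary methods in Section 12.1 carry no such deferral.

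**The concern.** Censoring at last contact gives a valid survival estimate only if those lost have the same later risk as those still followed. In heart failure, the subjects who stop attending may be the sicker ones. The attrition allowance is twice the expected mortality (20% / 10% = 2), so at that level of loss the unknown outcomes would outnumber the expected deaths.

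No randomised comparator shares the bias: each claim is one estimate against a fixed 80%. Death is also an outcome that a treating hospital's chart can often settle. Section 10.2, read as written, gives that information up even where consent still stands. What is at stake is the error rate of the survival claim in two of the cohorts.

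**Working it through.** **1. The plan's own figure.** Inputs from Table 12.1-1: goal 80%, expected survival 90%, power 90%, and "Hypothesis test based on a one-sided alpha level of 0.025". The smallest n by exact binomial is 137. Success needs at least 119 alive, with P(X ≥ 119 | 0.80) = 0.0245 and power P(X ≥ 119 | 0.90) = 0.910. Inflating gives 137 / 0.80 = 171.25, so 172. Both figures match the plan. Twenty per cent of 172 is 34.4, so about 34 subjects.

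**2. Model for informative loss.** Time is in years.
- Loss rate c = −ln(1 − 0.20) = 0.2231. This is loss in the absence of death, so about 31 of 172 are actually seen as lost.
- Death hazard is h during follow-up and k·h after loss. **k is an assumption.** The documents give no value, so a range is shown.
- True survival: S(1) = e^−(h+c) + ∫₀¹ c·e^−(h+c)t · e^−kh(1−t) dt. Set S(1) = 0.80 and solve for h.
- Kaplan-Meier with censoring at loss estimates e^−h instead.

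Pass rates come from simulating the planned rule, 20,000 trials per setting, with standard error at most 0.35 points. Smaller runs of 4,000 to 6,000 trials agree within simulation error; for k = 2 and 172 subjects they range from 5.0% to about 6%.

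| Loss | k | h | Kaplan-Meier target | Pass, 172 | Pass, 300 |
|---|---|---|---|---|---|
| 20% | 1 | 0.2231 | 80.0% | 1.9% | 2.1% |
| 20% | 2 | 0.2032 | 81.6% | 5.5% | 8.3% |
| 20% | 3 | 0.1881 | 82.9% | 11.4% | 19.3% |
| 20% | 5 | 0.1659 | 84.7% | 27.8% | 47.5% |
| 10% | 2 | 0.2130 | 80.8% | 3.4% | 4.5% |
| 10% | 3 | 0.2047 | 81.5% | 5.0% | 7.9% |

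Every row has true survival of exactly 80%, so the pass rate is the type I error. It is worse at 300 because a larger sample shrinks the standard error but not the bias.

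**3. Tipping counts at 172 subjects.** The log-log bound is L = S^exp(1.96·se), with se = √(Greenwood sum) / |ln S|. With complete data and 24 deaths: S = 148/172 = 0.8605, Greenwood sum = 24 / (172 × 148) = 0.000943, se = 0.0307 / 0.1503 = 0.204, L = 0.8605^1.492 = 79.9%, which fails. The exact binomial bound is 79.95%. With 23 deaths L = 80.6%, which passes. So 24 known deaths is the failure point.

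With 34 lost, and deaths and losses spread evenly over the year:

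| Observed deaths | Kaplan-Meier | Bound | Hidden deaths that make it fail | Expected at equal risk | Implied k |
|---|---|---|---|---|---|
| 15 | 90.2% | 84.3% | 9 of 34 (26%) | 1.7 | 6.3 |
| 17 | 88.9% | 82.8% | 7 of 34 (21%) | 1.9 | 4.1 |
| 20 | 87.0% | 80.5% | 4 of 34 (12%) | 2.3 | 1.8 |

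The hidden count is 24 minus the observed deaths. Implied k solves Σ[1 − e^−kh(1−t)] = hidden deaths over the 34 loss times t, with h = −ln(Kaplan-Meier). Twenty is the largest observed count that still passes.

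**4. The synopsis estimator.** Suppose lost subjects stay in the denominator as not alive. With 34 lost and 14 deaths (10% of the 138 followed), survival is 124/172 = 72.1% and the lower bound 64.7%. The test fails, so loss pushes the result the opposite way.

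**The case against.** The strongest case on the other side has five parts.

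- **Censoring is standard and holds its level when loss is unrelated to risk.** This stands. The k = 1 rows show about 2%, within the nominal 2.5%.
- **A reader might infer that modest loss makes a failing cohort pass.** The figures do not support that. At true survival of 80%, 20% loss and k = 2, the test still fails about 94% of the time at 172 subjects. In the 17 + 7 example the cohort has 86% survival, above the goal; only the bound slips under 80%, and it takes about a fourfold hazard. At the planned 10% mortality (about 15 observed deaths) it takes about sixfold. For a just-passing result to hide true mortality of 20%, 15 of the 34 lost must have died (20 + 15 = 35; 35/172 = 20.3%), about a ninefold hazard. Only a borderline result turns on a small excess.
- **A reader might infer that the plan tolerates 20% loss.** Section 12.1.6 uses the figure to inflate 137 to 172. It is neither a forecast nor a permitted rate, and actual loss may be lower.
- **Subjects withdrawn by the study are a separate matter.** The subject-level withdrawals described are for ineligibility (Sections 9.1 to 9.3 and 10.1). Sections 9.1 and 12.2.1 keep these subjects out of the analysis, so collecting their vital status would not change the result.
- **Some safeguards exist.** These are tracing by calls and letter, six-monthly visits, Latitude reports for PM/CRT-P devices, and the device-related exception. They may reduce loss. None yields vital status once a subject has been withdrawn as lost, and the Non-device cohort has no remote monitoring.

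These points limit the size of the problem. They do not answer why deaths that could be known should be discarded under a stated rule, or why no check on the assumption is planned.

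**Conclusion.** The point holds as a risk to the error rate of two primary tests, and should be fixed. Under informative loss the Kaplan-Meier test against 80% leans towards passing. At true survival of 80% and 20% loss, the false-pass rate is about 5 to 6% (172 subjects) and 8% (300) for a twofold hazard after loss, and about 11 to 12% and 19 to 20% for threefold. With 10% loss and a twofold hazard it is about 3.5% and 4.5%.

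This rests on an assumed multiplier, constant hazards, loss spread over the year, and loss at the planning allowance; it also supposes that lost subjects are sicker, not healthier. Nothing in the documents shows that loss will be informative or will reach 20%. The direction applies to the estimator in Section 12 and not necessarily to the one in the synopsis, so the two need to be settled together.

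**What to change.** 1. **Section 10.2.** Limit the bar on further data to subjects who withdraw consent. For eligible subjects lost to follow-up, obtain 12-month vital status from the treating hospital's records, with matching wording in the consent form.
2. **Sections 12.1.3.2 and 12.1.4.2.** Pre-specify a tipping-point analysis: apply a rising hazard multiplier after censoring until the lower bound reaches 80%, with all lost subjects counted as dead as the bounding case. Report it beside the primary result, with the number lost. It also covers subjects who withdraw consent, whose status stays unknown.
3. **Synopsis, Statistical Test Method.** Replace the proportion alive with the Kaplan-Meier estimator of Section 12, or state which one governs and how lost subjects count.

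The cost is protocol and consent wording with ethics committee approval, a chart check for those lost, and one extra analysis. The sample size does not change.

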12.1.5. Secondary Endpoints

- The secondary endpoint for subjects implanted with CRT-D/ICD is:
 - All-cause mortality rate
- The secondary HF endpoints for subjects with device implanted include:
 - Composite rate of HF events in ICD, CRT-D, and PM/CRT-P cohorts, which require IV treatment, HF related hospitalization, or led to HF death
 - Therapeutic sustainability at 1 year in ICD, CRT-D, and PM/CRT-P cohorts, defined as free of qualified SADEs post successful implantation, such as re-implant procedure, required invasive procedure related to the device system, pacing exit block, all-cause infection, and death due to therapy failure in comparison with data from MADIT CRT, MADIT RIT, Optimind, and Rally X4 studies.
- The secondary endpoint for subjects implanted with CRT-D/ICD and non-device subjects is:
 - Comparison of rate of sudden cardiac death in the non-device cohort with the rate of appropriately treated ventricular arrhythmias or sudden cardiac death in the defibrillator cohort (ICD cohort and CRT-D cohort)

Secondary analyses will be descriptive and exploratory. Detailed statistical methods for these endpoints will be presented in a Statistical Analysis Plan (SAP).

12.1.6. Sample Size

The pre-specified primary endpoints sample sizes are outlined in **Error! Reference source not found.** The minimum required sample sizes to sufficiently power each primary endpoint at 90% and account for up to 20% attrition are lower than the final sample sizes.

The final sample sizes for the device cohorts (ICD: 117 to 270 subjects; CRT-D: 95 to 250 subjects; PM/CRT-P: 172 to 200 subjects) will ensure that there will be a sufficient number

of subjects to evaluate each primary endpoint, as well as provide ample data to characterize the safety, performance and efficacy profiles based on secondary and additional endpoints.

The final sample size for the non-device cohort (Non-device [ESC Guideline 2016 Indicated but not implanted]: 172 to 300 subjects) will ensure that there will be a sufficient number of subjects to compare the rate of sudden cardiac death in the non-device cohort with the rate of appropriately treated ventricular arrhythmias or sudden cardiac death in the defibrillator cohort (ICD, CRT-D).

In case of low enrollment rates, enrollment may be closed after the statistically required calculated minimum sample size was completed.

Table 12.1-1: Endpoint Sample Size Estimates

Endpoint	Measurement	Performance Goal Hypotheses ¹	Expected Performance ²	Power	Number of Subjects	
					Needed for Analysis	Required Minimum Sample size Enrolled for ≤20% Attrition
Primary Endpoint for ICD Treated Subjects	Ventricular arrhythmia ³ associated symptoms free-rate from 0 to 12 months	H_0 : Rate ≤ 85.0% H_A : Rate > 85.0%	95.0%	90%	93	117
Primary Endpoint for CRT-D Treated Subjects	Ventricular arrhythmia ³ associated symptoms free-rate from 0 to 12 months	H_0 : Rate ≤ 87.0% H_A : Rate > 87.0%	97.0%	90%	76	95
Primary Endpoint for PM/CRT-P Treated Subjects	All-cause mortality free-rate (survival rate) from 0 to 12 months	H_0 : Rate ≤ 80.0% H_A : Rate > 80.0%	90.0%	90%	137	172
Primary Endpoint for Non-device Subjects (ESC Guideline 2016 Indicated but not implanted)	All-cause mortality free-rate (survival rate) from 0 to 12 months	H_0 : Rate ≤ 80.0% H_A : Rate > 80.0%	90.0%	90%	137	172

¹ Hypothesis test based on a one-sided alpha level of 0.025; clinically accepted delta of 10%, subtracted from expected performance

² Determined from prior comparable studies

³ Appropriately treated

CRT-D = cardiac resynchronization therapy-defibrillator; ICD = implantable cardioverter-defibrillator;

PM = pacemaker; CRT-P = cardiac resynchronization therapy-pacemaker.

Sample sizes for primary endpoints were calculated employing exact binomial methods in nQuery + nTerim 3.0.

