Statistical Test Method (continued)	
 • The primary endpoints above will be performed for ICD and CRT-D cohorts combined (primary analysis) as well as for ICD and CRT-D treated subjects separately (for descriptive purpose). • For PM/CRT-P treated subjects, the all-cause mortality free-rate (survival rate) from implant will be calculated as the proportion of actively enrolled subjects who are alive 12 months after implant. The null hypothesis will be rejected and the endpoint considered met if the lower one-sided 97.5% confidence bound for the proportion of subjects with no death is greater than 80.0%. • For Non-device subjects (ESC Guideline 2016 Indicated but not implanted), the all-cause mortality free-rate (survival rate) from enrolment will be calculated as the proportion of actively enrolled subjects who are alive 12 months after enrolment. The null hypothesis will be rejected and the endpoint considered met if the lower one-sided 97.5% confidence bound for the proportion of subjects with no death is greater than 80.0%. • Exploratory analyses for ICD and CRT-D Cohorts combined versus Non-Device Cohort (ESC Guideline 2016 Indicated but not implanted): propensity score matching comparison of all-cause mortality rate and composite rate of HF events between pooled cohorts with device (ICD and CRT-D) versus the Non-Device Cohort regarding 7 risk factors at baseline (NYHA Class III or IV, renal dysfunction [chronically BUN >26 mg/dL / ≥ 9.28 mmol/L], diabetes type I and II, chronic atrial fibrillation [permanent or persisting according to ESC Guideline 2016], prior MI, age >70 years, smoking today or during last 5 years). 
Further details on analytical methods can be found in Section 12 of the CIP

Sample Size Parameters	
ICD Treated Subjects:
 
The minimum required sample size to statistically power the ventricular arrhythmia associated symptoms free-rate through 12 months post implant is 117 subjects. Sample size was calculated assuming a 95.0% ventricular arrhythmia associated symptoms free-rate, a performance goal of 85.0%, one-sided alpha level of 0.025, 90% power, and 20% attrition.

Heart Failure Indication and Sudden Cardiac Death Prevention Trial Japan
Hinode

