12.1.1.2. Statistical Methods

When the final study subject reaches the final CIP required follow-up visit, the primary analysis will be performed based on the Kaplan-Meier method for the estimation of the 12-month ventricular arrhythmia associated symptoms free-rate, including the lower 97.5% confidence bound (computed based on log-log methodology). This Kaplan-Meier analysis will begin at the time of implant. Subjects that withdraw consent or are lost-to-follow-up prior to the 12-month endpoint evaluation will be censored at their date of last contact. All subjects actively enrolled will be included in the endpoint analysis.

The null hypothesis will be rejected and the endpoint considered met if the lower 97.5% confidence bound for the ventricular arrhythmia associated symptoms free-rate at 12 months is greater than 85.0%.

Additionally, a Kaplan-Meier survival time-to-event curve along follow-up will be provided.

The primary analysis above will be performed for CRT-D and ICD cohorts combined as well as for ICD treated subjects separately.

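### The 90% power in Table 12.1-1 is that of an exact binomial test; under the Kaplan-Meier log-log rule that decides success, power at the analysed sizes is about 82% (ICD), 81% (CRT-D) and 86% (PM/CRT-P, Non-device)

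*Combined protocol and SAP*

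**What the plan says.** Section 12.1.6 introduces the sizes as follows: "The minimum required sample sizes to sufficiently power each primary endpoint at 90% and account for up to 20% attrition". Table 12.1-1 gives 90% power for each of the four primary endpoints, with 93 (ICD), 76 (CRT-D), 137 (PM/CRT-P) and 137 (Non-device) subjects analysed and enrolment minima of 117, 95, 172 and 172. The note under the table reads: "Sample sizes for primary endpoints were calculated employing exact binomial methods in nQuery + nTerim 3.0". The first footnote adds: "Hypothesis test based on a one-sided alpha level of 0.025; clinically accepted delta of 10%, subtracted from expected performance". The Synopsis (Sample Size Parameters) repeats the basis for each cohort: "one-sided alpha level of 0.025, 90% power, and 20% attrition".

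The decision rule is in Sections 12.1.1.2, 12.1.2.2, 12.1.3.2 and 12.1.4.2. Each uses the Kaplan-Meier estimate of the 12-month event-free rate, "including the lower 97.5% confidence bound (computed based on log-log methodology"), and declares the endpoint met if that bound exceeds the goal. Withdrawals and losses before 12 months are censored at last contact, and all actively enrolled subjects stay in the analysis.

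The Synopsis (Statistical Test Method) describes a simple proportion with a lower 97.5% bound and does not name the method for the bound. No section gives power for the log-log rule.

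**The concern.** An exact binomial bound and a log-log bound are different decision rules. With few events and fewer than 150 subjects, a shift of one event in the pass mark moves power by several percentage points. If the rule in Section 12.1 is stricter than the rule used for sizing, the stated chance of meeting each goal is too high. The risk is a missed goal when the planning rate is true: 10% on the table's account, but nearer 19% for ICD and CRT-D at the table's own analysed sizes.

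A second gap bears on the same figures. With no events the log-log transform is undefined, and the plan does not say whether such a result meets the goal. At the CRT-D planning rate this is not a rare outcome.

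**Working it through.** **Inputs.** One-sided alpha 0.025. Goals and planning rates from Table 12.1-1 and the Synopsis (for ICD: "Sample size was calculated assuming a 95.0% ventricular arrhythmia associated symptoms free-rate, a performance goal of 85.0"%): 85%/95% ICD, 87%/97% CRT-D, 80%/90% PM/CRT-P and Non-device. Analysed sizes 93, 76, 137; enrolled minima 117, 95, 172.

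**Step 1: reproduce the table.** The exact test passes with at most c events, where c is the largest count with P(X ≤ c) ≤ 0.025 at the goal. Power is P(X ≤ c) at the planning rate.

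| Cohort | n | c | Type I error | Power |
|---|---|---|---|---|
| ICD | 93 | 7 | 2.35% | 90.6% |
| CRT-D | 76 | 4 | 2.41% | 92.2% |
| PM/CRT-P, Non-device | 137 | 18 | 2.45% | 91.0% |

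Each n is the smallest that reaches 90%, and n/0.8 rounded up gives 117, 95 and 172. The table is correct for the exact test.

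**Step 2: apply the log-log rule at the same counts, complete data.** With e events among n subjects, S = 1 − e/n, se = √[e/(n(n − e))], and the lower bound is L = S^exp(1.96·se/|ln S|).

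- ICD 7/93: S = 0.9247, se = 0.0296, L = 84.86%, below 85%.
- CRT-D 4/76: S = 0.9474, se = 0.0270, L = 86.58%, below 87%.
- PM/CRT-P, Non-device 18/137: S = 0.8686, se = 0.0332, L = 79.96%, below 80%.

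All three fail. With one event fewer the bounds are 86.20%, 88.26% and 80.80%, and all pass. The log-log pass marks are therefore 6, 3 and 17.

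**Step 3: power and type I error of the log-log rule at these sizes.**

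| Cohort | n | Max events | Type I error | Power, zero events met | Power, zero events not met |
|---|---|---|---|---|---|
| ICD | 93 | 6 | 1.0% | 81.6% | 80.8% |
| CRT-D | 76 | 3 | 0.8% | 80.6% | 70.7% |
| PM/CRT-P, Non-device | 137 | 17 | 1.4% | 86.0% | 86.0% |

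The last column subtracts the chance of no events: 0.95^93 = 0.8%, 0.97^76 = 9.9%, and a negligible amount at 0.90^137.

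**Step 4: how far it extends over n.** Comparing the two pass marks at every n from the analysed to the enrolled size, with complete data, they differ only at:

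- ICD: 93, 102, 110, 111 (4 of 25 sizes)
- CRT-D: 76, 77, 78, 87, 88 (5 of 20)
- PM/CRT-P, Non-device: 137, 143, 149, 155, 161 (5 of 36)

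With zero events counted as met, the log-log rule first reaches 90% at 94, 79 and 138, and stays above it from 112, 89 and 150.

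**Step 5: enrolled minima.** The loss patterns are assumptions, since the plan gives none. The evenly spread case is simulated with a constant event hazard; the other two follow from the binomial distribution. Zero events counts as met.

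| Pattern at 117 / 95 / 172 | ICD | CRT-D | PM/CRT-P, Non-device |
|---|---|---|---|
| No loss | 93% | 93% | 94% |
| Each subject lost with 20% probability, evenly over the year | 90% | 89% | 92% |
| Each subject lost with 20% probability, no follow-up at all | 86% | 83% | 88% |

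If zero events does not count as met, CRT-D is about 88%, 82% and 73% in the three rows. ICD changes by less than one percentage point.

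**The case against.** The strongest reply is that 93, 76 and 137 complete subjects is not the dataset the plan expects. It enrols at least 117, 95 and 172, keeps everyone in the analysis and censors losses at last contact, so partial follow-up is used. On that footing power is close to 90% or above, and at the upper enrolment limits it is higher still. The gap at the table's sizes is also a discreteness effect that one to three extra subjects would remove. All of this stands, and it limits the point to a mis-stated figure.

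A reader might go further in four ways that the documents do not support.

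- **CRT-D power is 71%.** That holds only if a zero-event result counts as a failure. The plan does not say so; it is silent.
- **Attrition leaves no partial follow-up, because Section 9.1 removes ineligible subjects from the analysis.** The 556 at which enrolment may close is a count of eligible subjects (117 + 95 + 172 + 172), and Section 10.3 keeps consent-ineligible subjects out of the enrolment ceiling. Only ineligibility found after closure, or loss straight after enrolment, behaves this way. The no-follow-up row is the unfavourable end of the range.
- **The 90% claim is wrong even for the exact test.** Exact power does dip to 86.7% (ICD, n = 101), 88.3% (CRT-D, n = 86) and 88.3% (PM/CRT-P and Non-device, n = 142). That is the usual sawtooth of exact tests, not a fault of this plan.
- **False success is more likely.** The opposite is true at these sizes: the log-log rule is conservative.

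The Synopsis also makes the combined ICD and CRT-D analysis primary and the separate cohorts descriptive, which would reduce the weight of those two shortfalls. But it gives no combined goal or power, so the cohort figures are the only power the plan states for the defibrillator endpoint.

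**Conclusion.** The point holds in a limited form. The 90% in Table 12.1-1 is correct for the exact binomial test and wrong for the rule in Sections 12.1.1.2 to 12.1.4.2. At the analysed sizes with complete data the rule has power of about 82% (ICD), 81% (CRT-D) and 86% (PM/CRT-P and Non-device), counting zero events as met. These figures follow from the binomial distribution and the plan's own rates.

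At the enrolled minima the shortfall largely disappears if losses are spread over the year, and there is none without loss. It persists, at 86%, 83% and 88%, only if losses contribute no follow-up. The part that does not fade is the undefined zero-event result in CRT-D. It is worth about 10 percentage points at 76 subjects and about 7 at 95 with evenly spread loss (89% against 82%). No conclusion of the trial would be invalidated; a stated operating characteristic needs correcting.

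**What to change.** In Table 12.1-1, Section 12.1.6 and the Synopsis, state power for the Kaplan-Meier log-log rule. Give it at the analysed sizes (82%, 81%, 86%, 86%) and at the enrolled minima, with the loss pattern assumed for the 20% attrition. Keep the exact binomial calculation as the basis on which the sizes were chosen, and label it so.

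In Sections 12.1.1.2 to 12.1.4.2, state that a zero-event result counts as goal met, for example by using the exact binomial lower limit in that case. Then the figures above, with zero events counted as met, apply.

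The cost is wording in one table and a few paragraphs. No extra subjects are needed, and the stated power at the analysed sizes becomes less favourable.

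Replacing the log-log bound by a beta product bound is an optional alternative. It equals the exact limit when nobody is censored, so sizing and test would agree, and it covers zero events. Its power under the planned censoring has not been shown and should be before it is adopted.
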